Active cooling will be achieved by embedding a TEC assembly into a standard prosthetic socket and liner. The TEC assembly is comprised of a thermoelectric cooling unit (TEC), heat sink, fan and heat spreader and has previously been tested under New England IRB (NEIRB) protocol NEIRB # 120160413/HRPO Log A-17885.2. An experimental socket with the integrated heat spreader will be fabricated for each amputee subject. The amputee subjects will either visit their prosthetist's office

Figure 1. TEC Module embedded into standard prosthetic socket for active cooling condition.

or LTI's in-house prosthetist for measurements and the new socket will be fabricated. The subjects may return for alignment and adjustment on the new socket.

Testing will measure the temperature, humidity, socket suspension and moisture accumulation of the limb when active cooling, moisture/thermal management, and no cooling is applied in order to determine the effectiveness of the proposed technology.

Walking will be used to increase the temperature of the limb in order to measure the system's ability to cool it as well as to determine subject perception of heat and comfort with the experimental liner and active cooling system as compared to the control liners and sockets.

Research participants will have socket temperature and moisture data collected while walking on a treadmill in the different conditions throughout different site visits. The active cooling from the ICE module will be completed with the experimental liner as well as with the control liner. The order of conditions with the experimental and control liners and the active cooling on or off will be randomized for each subject.

5. Study Population

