The subject will then perform in-laboratory testing to determine the effectiveness of an experimental liner to keep the limb cooler and dryer as compared to the control prosthetic liner. The order of conditions (Experimental Liner versus Control Liner, with or without the active cooling ICE unit) will be randomized.

Similar to what was done in a prior protocol under a previous effort (NEIRB # 120160413/HRPO Log A-17885.2), an array of temperature sensors will be attached to the subject’s residual limb before donning the socket and/or liner to give a more complete picture of the overall temperature distribution across the residual limb. Baseline readings will be taken of the residual limb temperature, the body’s core temperature via an oral thermometer, and the ambient temperature.

In addition, we will measure the amount of perspiration produced during each condition. The limb will be dried with a towel, so pre- and post-activity weight of the liner and towel will be measured and the difference in weight is attributed to the sweat produced during that condition as described by Wernke et al. [7]. Testing may also be performed in a thermal chamber that regulates the temperature of the testing area, such as that used by Klute et al. [8], to ensure that the subject will perspire.

In addition, humidity sensors will be attached to the subject's residual limb before donning the socket and/or liner similar to work completed by Cutti et al. [9]. These will allow a more complete picture of the onset of moisture on the residual limb during activity.

In addition, marks will be made with a skin safe marker on the leg where the top of liner rests before the subject begins the testing activity (such as walking on a treadmill). Once the testing activity has ended, the same mark will be made on the leg where the top of the liner rests. The distance between these lines will show any slippage that occurred during the activity which may be due to a lack of suspension.

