The subject will be asked to do the following tasks, similar to Klute et al. [3]: (1) an initial seated rest for up to 60 minutes to obtain baseline in-socket temperature data; (2) an activity to increase their body temperature, such as walking on a treadmill [2, 3] for up to 30 minutes; (3) a seated rest for up to 60 minutes; and (4) the liner and perspiration will be collected off the limb (with a towel) and weighed for changes. The second condition will begin once baseline temperatures have been reached and the test procedure repeated in the other condition

Throughout the in-lab test sessions, photos and/or videos may be taken to document such things as the location of the sensors on the limb, the temperature gradients across the limb (with a thermal camera), etc. At the end of each condition, subjective feedback on the comfort and temperature regulation of each condition will be obtained via a questionnaire developed during this effort. The participants would fill out the questionnaire rating parameters such as perceived comfort, intra-socket temperature, potential loss of suspension, etc.

This visit will take up to 4 hours.

This visit can be repeated at the subject's volition, if more data is required or if re-testing is needed.

Visit 3: The same tasks as described in Visit 2 will be completed using the same data collection process. The order of conditions (Experimental Liner versus Control Liner, with or without the active cooling ICE unit) will be randomized. The subject will perform in-laboratory testing to determine the effectiveness the ICE unit to cool and reduce moisture generation of a residual limb with an experimental liner as compared to with a standard control prosthetic liner.

We expect to demonstrate that even if the socket doesn't reduce the temperature during walking, it can cool the socket immediately upon cessation of walking, unlike the standard socket that produces the sustained high temperatures observed by Klute, et al. [3] and Huff, et al. [2]. This benefit is expected to increase with the addition of the experimental thermally conductive liner.

This visit will take up to 4 hours.

This visit can be repeated at the subject's volition, if more data is required or if re-testing is needed.

Once all testing is completed, the research participant will complete a questionnaire to describe their opinions on the comfort, look, and functionality of the experimental liner and ICE unit.

8. Study Conduct

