The data collected in the laboratory will include limb temperature, ambient temperature, limb humidity, ambient humidity, and moisture generation on the limb. Standard outcomes measures will include: Dermatology Life Quality Index, Modified Dermatology Life Quality Index, the Residual Limb Health section of the Prostheses Evaluation Questionnaire (PEQ), and the EuroQol-5D. Custom questionnaires that were developed to assess the experimental liner and ICE system will also be used.

The primary outcome of this study will assess the effect of the experimental liners on the temperature of the residual limb; however secondary measures include moisture generation and humidity on the residual limb as well as satisfaction with the prosthesis using the above measures. Measures during the experimental liner conditions will be compared to the control conditions both with and without the ICE system being active.

15. References

- [1] J. T. Peery, W. R. Ledoux, and G. K. Klute, "Residual-limb skin temperature in transtibial sockets," *The Journal of Rehabilitation Research and Development*, vol. 42, no. 2, pp. 147–154, 2005.
- [2] E. A. Huff, W. R. Ledoux, J. S. Berge, and G. K. Klute, "Measuring Residual Limb Skin Temperatures at the Skin-Prostheses Interface," *JPO Journal of Prosthetics and Orthotics*, vol. 20, no. 4, pp. 170–173, Oct. 2008.
- [3] G. K. Klute, E. Huff, and W. R. Ledoux, "Does Activity Affect Residual Limb Skin Temperatures?," *Clinical Orthopaedics and Related Research®*, vol. 472, no. 10, pp. 3062–3067, Jun. 2014.
- [4] A. Finlay and G. Khan, "Dermatology Life Quality Index (DLQI)-a simple practical measure for routine clinical use," *Clinical and Experimental Dermatology*, vol. 19, no. 3, pp. 210–216, 1994.
- [5] H. Meulenbelt, J. Geertzen, M. Jonkman, and P. Dijkstra, "Skin Problems of the Stump in Lower-limb Amputees: 2. Influence on Functioning in Daily Life," *Acta Dermato Venereologica*, vol. 91, no. 2, pp. 178–182, 2011.
- [6] D. A. Boone and K. L. Coleman, "Use of the Prostheses Evaluation Questionnaire (PEQ)," *JPO Journal of Prosthetics and Orthotics*, vol. 18, no. Proceedings, 2006.

- [7] M. M. Wernke, R. M. Schroeder, C. T. Kelley, J. A. Denune, and J. M. Colvin, "SmartTemp Prosthetic Liner Significantly Reduces Residual Limb Temperature and Perspiration," *Journal of Prosthetics and Orthotics*, vol. 27, no. 4, pp. 134–139, Oct. 2015.

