The fourth measure we will be using is a subscale of the validated Prostheses Evaluation Questionnaire (PEQ) [3]. The PEQ consists of 82 items grouped into nine subscales, each addressing a different aspect of prosthesis wear (pain, satisfaction, comfort, etc.). The PEQ scales are not dependent on each other, so it is reasonable to use only those scales of interest. We will be using the Residual Limb Health section which rates qualities such as in-socket perspiration and skin breakdown of the residual limb. For each scale used, all of the individual questions that make up that scale must be included. The questions refer to the prior 4 weeks and are scored using a visual analog scale (100mm line). There is no total score. A guide gives coding instructions for all questions and groups the questions under different subscales. Each subscale score is computed by excluding any unanswered questions and averaging the answers within each subscale.

Visit #2 & Visit #3 – Part #1 & Part #2 – Individual Liner Questionnaire

The custom individual liner questionnaire was developed to rate the different aspects of the experimental and control liner. This questionnaire will be completed immediately after each activity to rate the liner that was used during that activity.

Visit #2 & Visit #3 – Part #3 – Liner Comparison Questionnaire

The custom liner comparison questionnaire was developed to measure the subject's preference for different criteria between the experimental and standard liner. This questionnaire will be completed at the end of Visit #2 and Visit #3 after the subject has completed both sets of activities.

References

- [1] A. Finlay and G. Khan, "Dermatology Life Quality Index (DLQI)-a simple practical measure for routine clinical use," *Clinical and Experimental Dermatology*, vol. 19, no. 3, pp. 210–216, 1994.
- [2] H. Meulenbelt, J. Geertzen, M. Jonkman, and P. Dijkstra, "Skin Problems of the Stump in Lower-limb Amputees: 2. Influence on Functioning in Daily Life," *Acta Dermato Venereologica*, vol. 91, no. 2, pp. 178–182, 2011.
- [3] D. A. Boone and K. L. Coleman, "Use of the Prosthesis Evaluation Questionnaire (PEQ)," *JPO Journal of Prosthetics and Orthotics*, vol. 18, no. Proceedings, 2006.

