7. how socket suspension felt while walking with this liner	 1 Leg Came Out	 2	 3	 4	 5 No Movement
8. how confident you felt that you would not slip out of this liner	 1 Not at All	 2	 3	 4	 5 Very Confident
9. how you would want a product like this for daily use	 1 Not at All	 2	 3	 4	 5 Very Much

10. Please provide any additional comments you feel might be useful to note:

Visit #2 – Part 3 – Comparison Questionnaire

ICE Unit: Off / ON

As you read through each question, remember there is no right or wrong answer. Just check off which prosthetic liner, if any, you prefer for each criterion listed below. It will be most helpful if you are completely truthful with your answers.

Criteria	Experimental	Control	No Preference
1. Ease of donning and doffing			
2. Ability to stand/walk			
3. Comfort while sitting			
4. Comfort while walking			
5. Comfort while standing			
6. Limb sweating			
7. Overall temperature in the socket			
8. Friction/Skin Comfort			
9. Slipping in socket			
10. Overall comfort			
11. Overall preference			

12. What did you **like** about the experimental liner and/or protocol?

13. What did you **dislike** about the experimental liner and/or protocol?

14. Other comments.

Visit #3 – Part 1 – Individual Questionnaire

Liner: Control / Experimental

ICE Unit: Off / ON

Fill in the circle that best describes the liner you just walked with:

On a scale from 1-5 please rate:					
1. your comfort while standing with this liner	 1	 2	 3	 4	 5 Excellent
2. your ability to stand with this liner	 1	 2	 3	 4	 5 Excellent
3. your comfort while walking with this liner	 1	 2	 3	 4	 5 Excellent
4. your ability to walk with this liner	 1	 2	 3	 4	 5 Excellent

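### The purposes given to Visits 2 and 3 do not fit the rule that ICE on/off order is randomized, and the protocol does not say how ICE state is assigned to visits

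*Protocol*

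**What the plan says.** **Randomization rule.** Protocol Section 4 states: "The order of conditions with the experimental and control liners and the active cooling on or off will be randomized for each subject". Section 7 repeats the rule in the same words in both the Visit 2 and the Visit 3 text: "The order of conditions (Experimental Liner versus Control Liner, with or without the active cooling ICE unit) will be randomized".

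**Visit purposes.** The Visit 2 testing is "to determine the effectiveness of an experimental liner to keep the limb cooler and dryer as compared to the control prosthetic liner"; ICE is not part of that purpose. The Visit 3 testing is "to determine the effectiveness the ICE unit to cool and reduce moisture generation of a residual limb with an experimental liner", and the sentence goes on to set this against the standard control liner.

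**Runs per visit.** The Visit 2 text describes two runs: "The second condition will begin once baseline temperatures have been reached and the test procedure repeated in the other condition". Visit 3 repeats the same tasks. The four combinations of liner and ICE state are therefore spread over two visits of two runs each.

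**Forms.** Appendix A says of the liner comparison questionnaire: "This questionnaire will be completed at the end of Visit #2 and Visit #3 after the subject has completed both sets of activities". In Appendix B that form asks for a preference between experimental and control liner and carries a single entry, "ICE Unit: Off / ON", at each visit. The individual questionnaires carry the same entry for each run.

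**Comparisons.** Section 14 makes the liner effect on residual limb temperature the primary outcome and adds: "Measures during the experimental liner conditions will be compared to the control conditions both with and without the ICE system being active".

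**The concern.** If ICE order is randomized, some subjects have ICE on at Visit 2, and the two visits cannot have separate liner and ICE purposes for them. If the purposes are kept, ICE order is not random. The protocol does not say which governs. Nor does it say whether the units being ordered are two ICE states over visits or four conditions over four runs.

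This cannot be left to the analysis. Which state a subject receives at which visit is settled in the laboratory and cannot be recovered later. Visits can plausibly differ in ways that affect limb temperature: familiarity with liner, socket and treadmill, adjustment of the check socket first tried at Visit 2, sensors that are re-placed, and ambient conditions. If ICE state moves together with visit, the ICE on-minus-off difference carries all of these. If ICE states are mixed within visits, the liner comparison at a fixed ICE state loses the protection of being made on one day.

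**Working it through.** The protocol states no figure on this point to reproduce, so the check is on the structure of the design.

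**Inputs.** Four conditions (experimental or control liner, ICE off or on) and two test visits of two runs each (Section 7); one ICE entry per comparison form (Appendix B); 12 target subjects (Section 5), used only to size the check.

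**1. Count the orders.** Four conditions in four runs give 4! = 24 orders. The four conditions can be split into two visit pairs in 3 ways, and each split gives 2 × 2 × 2 = 8 orders (which pair comes first, and the order within each pair).

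| What the two runs of a visit share | Orders | Liner contrast at a fixed ICE state | Comparison form |
|---|---|---|---|
| ICE state | 8 | within a visit | fits |
| Liner | 8 | across visits | only one liner worn, nothing to compare |
| Neither | 8 | across visits | two liners, but two ICE states for one entry |

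Unrestricted randomization thus mixes ICE states within a visit in 8 + 8 = 16 of 24 orders (67%). Only 4 of 24 (17%) have ICE off throughout Visit 2 and on throughout Visit 3, the pattern that the visit purposes suggest.

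**2. What can be estimated.** Take 12 subject effects plus liner, ICE, liner × ICE, visit and position within visit: 12 + 5 = 17 columns.

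| Allocation | Rank | ICE separable from visit? | Liner estimable? |
|---|---|---|---|
| ICE off at Visit 2, on at Visit 3, for all | 16 of 17 | no | yes |
| ICE state randomized to visit | 17 of 17 | yes | yes |
| All four conditions randomized | 17 of 17 | yes | yes |

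In the first row the ICE and visit columns are identical. Liner × ICE remains estimable there only if the liner effect does not itself change between visits.

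**3. Size of the bias.** Let δ be the Visit 3 minus Visit 2 shift and p the share of subjects with ICE off first. The simple ICE on-minus-off difference has bias δ(2p − 1). The values of δ below are assumptions.

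| δ (assumed) | p = 1 | p = 0.75 | p = 0.5 |
|---|---|---|---|
| 0.2 °C | 0.2 | 0.1 | 0 |
| 0.5 °C | 0.5 | 0.25 | 0 |
| 1.0 °C | 1.0 | 0.5 | 0 |

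For scale, Section 1 cites a rise of 2 °C as possibly responsible for thermal discomfort.

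**4. False positives under the fixed order.** Assume also a two-sided 5% paired t-test, no true ICE effect, and a shift of d standard deviations of the paired difference. The rejection rate comes from the noncentral t distribution with n − 1 degrees of freedom and noncentrality d√n. For d = 0.25 it is 12% at n = 12 and 19% at n = 20; for d = 0.5 it is 35% and 56%. The test, the level and d are not in the protocol. These rates apply only if ICE is fixed by visit.

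**The case against.** A reader might infer that the protocol fixes ICE off at Visit 2 and on at Visit 3, so that the ICE effect is fully confounded with visit. The text does not support this. No sentence assigns an ICE state to a visit. The randomization rule appears three times, and in the Visit 3 text it stands directly before the purpose sentence. The forms for both visits leave the ICE state open, which would be needless if it were fixed. A purpose sentence is also not an allocation rule, and the Visit 2 purpose does not exclude ICE. All of this stands, so complete confounding is one reading only.

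A reader might also infer that the main result is at risk from a fixed order. It is not. Section 14 compares liners within each ICE state, and the Visit 3 question, read to its end, compares ICE with the experimental liner against ICE with the control liner. Both are within-visit liner contrasts under that reading. The expectation of cooling when walking stops is set against temperatures observed in earlier cited studies and can be read within a run, so it need not rest on the ICE on/off contrast.

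Baseline limb, core and ambient readings, the possible sensor template and the possible thermal chamber would shrink some visit differences. They do not undo aliasing.

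What remains is that the purposes and the rule point to different conduct, and that even the rule alone leaves open what is being ordered. Section 4 describes testing with and without active cooling, so the ICE on/off contrast is of interest although it is not primary.

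**Conclusion.** The point holds as an inconsistency to be reconciled: should-fix. The visit purposes and the randomization rule do not fit together, and each, taken alone, allows a poor design.

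- Followed by purpose, the secondary ICE on/off contrast is completely aliased with visit. Its bias equals the whole visit shift, and neither more subjects nor any model removes it. The within-visit liner contrast, and so the primary outcome, is not biased.
- Followed as unrestricted randomization of four conditions, every main effect is estimable, but in 16 of 24 orders the same-ICE liner contrast crosses visits and the comparison form cannot be completed as designed. This is not a systematic bias, since order is random; the contrast takes on between-visit variation.

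That ICE is meant to be constant within a visit is inferred from the two runs and the single ICE entry on the comparison form; the protocol does not say so outright. The counts and ranks follow from the design. The visit shifts and rejection rates are illustrative, because the protocol gives no visit effect, standard deviation or test.

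**What to change.** In Section 7, give Visits 2 and 3 one common purpose: to compare the experimental with the control liner under the ICE state assigned to that visit, and to compare ICE on with ICE off over the two visits. In Section 4 and in both visit texts, replace the order sentence with a two-step rule: ICE state (off first or on first) is randomized to visit for each subject, and liner order is randomized within each visit. This leaves the 8 orders that the comparison form fits, and all effects are estimable.

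A balanced list is preferable to independent draws. With 12 subjects, independent 1:1 draws give an exact 6:6 split of ICE order with probability C(12,6)/2^12 = 924/4096 = 23%, and a split of 9:3 or worse with probability 2 × (1 + 12 + 66 + 220)/4096 = 598/4096 = 15%. Imbalance costs precision and does not bring the aliasing back, so this is a refinement. Visit and period terms can be left to the analysis plan.

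**Cost.** Protocol wording and a randomization list; no extra runs, visits or subjects, and no change to the forms. The ICE unit must be ready by Visit 2 for subjects assigned to ICE on first. For amputees, the Visit 1 text already has the unit installed when the socket is made.

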Moisture Management Liner Effectiveness Study

Investigators	[name] Liberating Technologies, Inc. [name] [contact]
	[name] Vivonics, Inc. [name]
Sponsor	U.S. ARMY MEDICAL RESEARCH ACQUISITION ACTIVITY (USAMRAA)
Sponsor Protocol #	E00572.1a
Solutions IRB #	2020/01/01

1. Background and Introduction

The comfort and fit of the residual limb within a prosthetic socket are of primary concern for many amputees. The residual limb is typically covered by non-breathable and non-thermally conductive materials that can create a warm and ultimately moist environment. These layers consist of a prosthetic liner that rolls onto the limb and traps heat and occasional extra prosthetic socks. Studies found increases in socket temperature after the prosthesis was donned (0.8°C) [1] and after 30 minutes of walking (2.5°C) [2]. Temperatures were found to remain elevated long after activity cessation and even a rest period of double the duration of the preceding activity period is insufficient to return the limb to its initial temperature [3]. Peery, et al. [1] suggested that a modest temperature increase of only 2°C may be responsible for reports of thermal discomfort by amputees. Therefore, a small amount of activity can cause the socket temperature to elevate and remain at an uncomfortable level for an extended period of time, which can lead to decreased wear times. In summary, an uncomfortable socket/residual limb interface decreases prosthesis use among amputees who want to remain active in their lives.

To address this, Vivonics, Inc. and Liberating Technologies, Inc. (LTI) have developed a silicone liner approach to wick sweat from the skin and out of the socket through specially designed microchannels and to passively conduct heat from the skin using thermally conductive elastomers. This liner has been developed to work alongside a thermo-electric cooling (TEC)-based module called the Intrasocket Cooling Element (ICE) developed in a parallel project by Vivonics and LTI. The ICE device can be embedded into the prosthesis in order to cool the residual limb. A technology that can provide thermal control while retaining adequate suspension, weight, and other prosthetic characteristics would benefit many prosthesis wearers.

2. Study Rationale

This study will focus on investigating the efficacy of this novel moisture and thermal management (experimental) liner.

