Subjects will be consented and screened for eligibility criteria. If they decide to participate, an experimental liner will be made that fits the size and shape of their limb and an experimental socket to fit the experimental liner will be fabricated using standard prosthetic techniques.

Subjects may withdraw at any time by simply telling the investigators they wish to stop their participation.

If a subject withdraws from the study, the data that were collected from them can still be used, and the withdrawn subjects may be replaced with a new subject. Deviations from the protocol that increase risks for subjects will be reported to Solutions IRB and HRPO for approval prior to being implemented.

The consent process and all testing will be completed at the Liberating Technologies, Inc. research facility located in Holliston, MA. Approved study staff from Vivonics, Inc. may also be present during testing visits to provide technical support or monitor testing activities. During these visits approved study staff from Vivonics, Inc. may be in contact with the subjects.

Subjects will be compensated \$40 per hour for the 3 visits for the in-lab testing and prosthetist visits for an estimated total of \$400 (10 hours) per subject. Travel will also be reimbursed per mile at the current IRS federal rate.

9. Study Treatment

This is not a treatment study. The purpose of the study is to evaluate the effectiveness of a moisture removal and thermally conductive liner.

10. Evaluation of Adverse Events

Based on past testing and data collection, no adverse events are expected. Adverse events could include: discomfort or dermatological reaction to experimental liner materials or sensors in the socket, tripping while walking on the treadmill, overheating or overcooling due to controller, sensor, or battery malfunction of the ICE unit. These risks have been mitigated by using biocompatible materials and/or hypoallergenic tape with the sensors, using a spotter during walking tasks for in-lab testing, and standard thermal and electrical management techniques including thermal battery management, voltage/current limiting, and monitoring temperature during testing.

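### Nothing keeps staff of the liner's developers away while subjects complete the open-label comfort and preference forms, so the secondary satisfaction outcome is open to courtesy bias.

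*Protocol*

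**What the plan says.** **Who made the device.** Protocol Section 1 states that "Vivonics, Inc. and Liberating Technologies, Inc. (LTI) have developed a silicone liner approach to wick sweat from the skin". Both companies are therefore developers.

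**Who may be there.** Section 8 places everything with one of them: "The consent process and all testing will be completed at the Liberating Technologies, Inc. research facility". Of the other it says "Approved study staff from Vivonics, Inc. may also be present during testing visits to provide technical support or monitor testing activities", and then "During these visits approved study staff from Vivonics, Inc. may be in contact with the subjects". It sets no limit by run or by step of the visit.

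**What is rated, and when.** Under Visit 2, Section 7 says that "subjective feedback on the comfort and temperature regulation of each condition will be obtained via a questionnaire developed during this effort", and that "The participants would fill out the questionnaire rating parameters such as perceived comfort, intra-socket temperature, potential loss of suspension, etc". Visit 3 follows the same process. Appendix A says of the individual liner form: "This questionnaire will be completed immediately after each activity to rate the liner that was used during that activity". It places the liner comparison form at the end of Visits 2 and 3.

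**What the ratings are for.** Section 14 lists among the secondary measures "satisfaction with the prosthesis using the above measures". The primary outcome is residual limb temperature.

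**The concern.** A subject who has just walked in a prototype may be reluctant to mark it down while its makers look on or talk about it. The items in Appendix B invite this: comfort, warmth, sweat, confidence in the suspension, whether the subject would want the product for daily use, and which liner is preferred overall.

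If the pull exists, it acts on the experimental side of each paired comparison, so it goes in the direction that the study hopes to show. Randomising the order of conditions balances period effects. It does not balance an influence that comes from the subject knowing which liner the staff in the room have built. Nor can an analysis correct for it later if nobody recorded who was present.

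**Working it through.** The protocol gives no figure on this point, so there is no calculation to reproduce. The check sets the relevant sections side by side.

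1. **Are the ratings collected while developer staff may be present?** Yes. Section 7 places the rating at the end of each condition and Appendix A places it directly after the activity. On either timing it falls inside Visit 2 or Visit 3. The preference form closes each of those visits. Section 8 allows Vivonics staff at testing visits, and LTI is the host.

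2. **How much of the satisfaction outcome is exposed?** Appendix B has two individual forms and one comparison form at each of Visits 2 and 3.
   - Individual forms: 2 visits × 2 forms × 9 rated items = 36 ratings per subject.
   - Comparison forms: 2 visits × 11 criteria = 22 preferences per subject.
   - All 36 + 22 = 58 answers are given inside these visits.
   - The standard instruments (DLQI, its modified version, EQ-5D and the PEQ Residual Limb Health scale) appear only at Visit 1. Appendix A describes the quality-of-life surveys as concerning the current liner and given before testing. They cannot contrast the test conditions, so the between-condition part of satisfaction rests on the custom forms.

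3. **Does the subject know the condition?** The protocol describes no blinding. Each individual form has a field for the liner and one for the ICE state. The comparison form has columns headed with the two liner types, so a subject must know which was which in order to answer.

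4. **Is there any safeguard?** Subjects fill in the individual form themselves (Section 7), and the comparison form reassures them that no answer is wrong and asks for honesty (Appendix B). The protocol does not provide for private completion, an independent administrator, sealed return or a limit on conversation.

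5. **Which outcomes lie outside this route?** Under Section 7, temperature and humidity come from sensors, sweat from weighing the liner and towel, and slippage from marks on the skin. None is a self-rating.

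**The case against.** The strongest reply is that this is the ordinary limitation of an open-label rating, on a secondary outcome, in a small laboratory study. Subjects complete the forms themselves, the comparison form invites candour, and they would know the condition even in an empty room. Much of this stands. Private completion removes only the avoidable part of the bias, and the point ranks as a modest improvement.

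A reader might go further and infer that Vivonics staff will attend the experimental runs more often, because prototypes need technical support, so that a staffing effect follows the condition. The document does not support this:
- Section 8 gives monitoring as a second purpose, and that applies equally to control runs.
- Each visit holds two runs. The comparison form sets the experimental liner against the control liner under a single ICE setting, so as the forms are built both liner runs share one visit.
- Sections 4 and 13 describe a passive liner, and nothing says that it needs support.
- LTI, itself a developer, hosts every run.

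Uneven attendance remains possible, particularly between ICE-on and ICE-off visits, and the randomisation wording does not clearly exclude other pairings. It is not indicated.

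A practical objection also stands. Section 10 lists temperature monitoring during testing among the risk mitigations, and the individual form may be completed close to the seated rest in which data are still being collected. Sending all staff out of the room could conflict with that. Removing the condition fields from the form would make a rating impossible to link to its run.

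**Conclusion.** The point holds as a weakness of conduct. Section 8 permits developer staff to be present and in contact with subjects, the condition-labelled forms are completed in the same visits, and nothing keeps those staff from observing or discussing the answers. The likely direction favours the experimental device.

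The size cannot be estimated. The protocol gives no standard deviation for these items, no expected shift and no test for them. Any statement of how far the false-positive rate rises would rest on an assumed shift and an assumed spread, so none is offered. The conclusion assumes only that some subjects answer more kindly when the makers can see or hear them.

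A reader might also infer that the main result is compromised. It is not by this route, because limb temperature is measured by sensors. Only the secondary comfort and preference ratings are exposed.

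**What to change.** Add to Sections 7 and 8 of the protocol that:

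- the subject completes every individual and comparison form privately, out of view of developer staff (Vivonics or LTI) and without conversation with them, while any safety and temperature monitoring continues;
- the liner and ICE fields are filled in before the form is given to the subject, so that each rating stays linked to its run, and the completed form is handed over sealed;
- Vivonics staff attend either all or none of a subject's compared runs, and their presence is logged for each run;
- the ratings are reported as open-label.

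Restricting Vivonics alone would not be enough, because LTI is also a developer and runs the site.

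The cost is a few sentences of protocol text and a short log. Staff could not clarify an item on the spot, so a few may be left blank, and attendance becomes slightly less flexible. Subjects would still know which condition they had, which is why the open-label statement is needed as well.
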